15.4.2 Costs collected via participant cost questionnaires

Participant cost questionnaires (PCQ) will be developed and piloted. The PCQs will collect information on NHS resource use and patient out-of-pocket expenses. The PCQ has two parts: Part A collects information on patients' health service use; and Part B gathers information on patients' time and travel costs of attending different health services. In order to reduce recall bias, participants will be asked to complete the Part A of PCQ at 3 month intervals (at 3 and 6 month follow-up). The Part B of PCQ collects information on participants' latest visit to each of the listed services and the information will be used at aggregated level to produce unit cost for each arm, hence it will only be administered once at 6 month follow-up.

15.4.3 NHS Resource costs

In addition to the costs related to the intervention, NHS resource use will also include patients' use of primary and secondary care due to problems as a result of having a small renal tumour. Thus, participants will be asked about the number of hospital outpatient and inpatient visits, GP visits, nurse visits and other specialist visits in the Part A of the PCQ.

15.4.4 Patient out-of-pocket expenses

Patients' out-of-pocket expenses refer to any costs incurred by the participants associated with the treatment of small renal tumours. Part A of the PCQ will collect information on any private personal/health care participants may pay for, such as over the counter medications, and private health insurance. Part B of the PCQ will collect information on participants' travel and time costs for accessing NHS services.

15.4.5 Travel costs: Participants will be asked about their mode of transport and the costs associated with travelling to each service. Unit costs for each journey will be estimated from this data. For example, participants who travelled by car will be asked the approximate distance travelled and the cost of parking whilst participants who travel by bus will be asked the price of their one-way fare. Participants will also be asked to provide travel cost information for any relatives/carers that accompany them to each service.

15.4.6 Time costs: Participants will be asked the time spent travelling to and the time spent at each service and what activity they would have been undertaking during that time if not attending the health services. For example, a participant may have to take time off work or forego leisure time in order to attend each service. These data will be presented in their natural units, e.g. hours and minutes, and attached monetary value using standard economic conventions, e.g. the Department of Transport⁴⁴ estimates for the value of leisure time. Participants will be asked to provide the same information for any relative or carer who accompanied them to each service.

16. Statistical Considerations

As this is a feasibility study our aim is to provide the foundations for future research in this area and to ensure that a larger scale research project is feasible and acceptable. We therefore aim to make estimates of subject availability, the willingness of subjects to be randomised to a trial treatment, of the proportion of subjects enrolled who complete the trial, and to obtain the data necessary to inform a power/sample size calculation for a future definitive phase III trial. Our primary focus is therefore on descriptive statistics rather than hypothesis testing.

16.1 Sample Size

We aim to recruit a total of 60 patients (30 to the surveillance arm; 30 to the ablation arm). This figure is based on a recommendation by Lancaster (2004)⁴¹ with respect to the number of patients required to yield meaningful estimates of parameters of interest. With six or more centres participating in the pilot we believe that is feasible to approach up to 120 patients; assuming an achieved recruitment rate of no less than 50% this should give us the sixty patients that we need.

16.2 Statistical Analysis

The primary purpose of this feasibility study is to assess willingness to be randomised. It has not been designed to make an assessment of treatment efficacy, and sample sizes will be too small to make an interim assessment of efficacy. We anticipate that, even if the initial rates are disappointing, that the qualitative research might suggest improvements that could be made to recruitment procedures, hence we have not defined a stopping rule for futility. This trial does not involve the use of drugs and hence issues of toxicity are not expected to be a concern.

For this trial, we will determine interval estimates (using 95% confidence intervals) of key parameters of interest. These include:

- The proportion of patients who agree to be randomised.
- The proportion of patients receiving ablation who experience peri-operative complications.
- The proportion of patients for whom we can collect outcomes at 3 months 6 months post treatment.
- The standard deviation of the quality of life measures that will be used in the phase III trial.

We will also investigate the distribution of the quality of life scores at each time point with a view to inform the planning of future analyses. This will be done primarily by consideration of graphical displays of the data.

In addition we will assess whether the following criteria for evaluating the success of the pilot have been met:

- The upper 90% confidence interval for the proportion of patients recruited should exceed 50%. We should recruit at least 49 patients from 120 approached. This is based on a requirement that the underlying recruitment rate should be at least 50%. The exact 90% confidence interval corresponding to 49 successes from 120 Bernoulli trials is from 32.0% to 50.2%. (With 48 successes from 120 trials the upper interval drops to below 50%). Should we recruit less than 49 patients we would regard this as evidence that the recruitment rate was too low; the external validity of a randomised controlled trial would be questionable.

- The upper 90% confidence interval for the retention rate (the proportion of patients recruited who have been followed up) should be greater than or equal to 80%.

17. Compliance and Withdrawal

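### The recruitment threshold of 49 out of 120 rests on a 95% interval labelled as 90%, so 49 recruits fail the 90% criterion that the protocol states

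*Protocol*

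**What the plan says.** Protocol section 16.2 gives the recruitment success criterion in two forms.

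- As an interval rule: "The upper 90% confidence interval for the proportion of patients recruited should exceed 50" per cent.
- As a count: "We should recruit at least 49 patients from 120 approached".

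The count is justified by a required underlying rate ("This is based on a requirement that the underlying recruitment rate should be at least 50" per cent) and by a worked interval: "The exact 90% confidence interval corresponding to 49 successes from 120 Bernoulli trials is from 32.0% to 50.2" per cent. A parenthesis then places the boundary between 48 and 49: "With 48 successes from 120 trials the upper interval drops to below 50" per cent. The consequence of missing it is explicit: "Should we recruit less than 49 patients we would regard this as evidence that the recruitment rate was too low".

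Two further statements bear on the confidence level. Earlier in the same section, "we will determine interval estimates (using 95% confidence intervals) of key parameters of interest", and the first parameter listed there is the proportion agreeing to be randomised. The retention criterion that follows the recruitment criterion is set at 90%, against a benchmark of 80%, with no count or limits printed. The denominator of 120 comes from section 16.1, which considers it "feasible to approach up to 120 patients".

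**The concern.** The printed limits look too wide for a 90% interval on 49/120. If the label is wrong, the count of 49 does not implement the rule printed beside it.

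This is the only numerical criterion for recruitment. Recruitment and retention rates are the quantitative part of the primary outcome (section 9.1), and section 16.2 names willingness to be randomised as the primary purpose of the study. If the two forms of the rule disagree, a result between them can be called a success or a failure depending on which sentence is read, and that choice could be made after the data are seen. Fixing the criterion in advance is meant to prevent this.

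**Working it through.** **Inputs (Protocol 16.2).** n = 120; threshold count x = 49; interval method described as exact; level 90%; benchmark 50%.

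**Formula.** The exact (Clopper-Pearson) two-sided limits at level 1 − α are

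- lower = the α/2 quantile of Beta(x, n − x + 1)
- upper = the 1 − α/2 quantile of Beta(x + 1, n − x)

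For x = 49 and n = 120 these are Beta(49, 72) and Beta(50, 71).

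**Step 1: reproduce the printed figure.** The printed interval is 32.0% to 50.2%.

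| Level | Lower | Upper |
|---|---|---|
| 90% | 33.27% | 48.74% |
| 95% | 31.95% | 50.18% |

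The 95% limits round to the printed figures at both ends. The 90% limits miss by more than one percentage point at each end.

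**Step 2: could another 90% method give 50.2%?** The Wald, Wilson, Agresti-Coull, Jeffreys, mid-p and inverted exact test intervals at 90% have upper limits for 49/120 between 48.2% and 48.6%. A one-sided 90% upper limit, which is the upper end of the two-sided 80% interval, is lower still at 47.1%. No reading at 90% gives an upper limit above 50%.

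**Step 3: find the count that each level implies.**

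| Recruits of 120 | Exact 90% interval | Upper limit above 50%? | Exact 95% interval | Upper limit above 50%? |
|---|---|---|---|---|
| 48 | 32.5% to 47.9% | no | 31.2% to 49.3% | no |
| 49 | 33.3% to 48.7% | no | 31.95% to 50.2% | yes |
| 50 | 34.1% to 49.6% | no | 32.7% to 51.0% | yes |
| 51 | 34.9% to 50.4% | yes | 33.5% to 51.9% | yes |

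The smallest passing count is 49 at 95% and 51 at 90%. The statement about 48/120 is true at both levels, so it does not support the 90% label.

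**Step 4: cross-check with binomial tails.** The two-sided upper limit exceeds 50% when P(X ≤ x | p = 0.5) is greater than α/2.

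- P(X ≤ 48) = 0.0177
- P(X ≤ 49) = 0.0274, above 0.025 but below 0.05
- P(X ≤ 50) = 0.0412, still below 0.05
- P(X ≤ 51) = 0.0602, above 0.05

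This again gives 49 at 95% and 51 at 90%.

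**Step 5: effect on the decision.** P(pass) = P(X ≥ threshold) for X ~ Binomial(120, p). The difference is the chance of landing on 49 or 50, where the two forms disagree.

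| True rate p | Threshold 49 | Threshold 51 | Difference |
|---|---|---|---|
| 40% | 46.0% | 31.9% | 14.1 points |
| 45% | 84.4% | 73.9% | 10.5 points |
| 50% | 98.2% | 95.9% | 2.4 points |

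At a true rate of 50%, the chance of wrongly failing is 1.8% with 49 and 4.1% with 51.

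**Step 6: retention.** No count is printed, so its label cannot be checked. Assuming the target of 60 is recruited, the smallest number followed up whose exact upper limit reaches 80% is 43 at 90% (42 gives 79.6%) and 42 at 95% (41 gives 79.7%). Here the level moves the bar by one patient.

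**The case against.** The arithmetic is not in dispute; the objections concern the remedy and the weight of the point.

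- **The text may have meant 95%.** The printed limits, the count of 49 and the sentence about fewer than 49 all fit 95%, and the same section uses 95% for its other estimates, including the proportion agreeing to be randomised. Against this, 90% is printed three times: for the criterion, for the worked interval and for retention. Intent cannot be settled from the document. This stands, and both repairs should be put to the sponsor.
- **The reach is narrow.** The two forms disagree only at 49 or 50 recruits from exactly 120 approached, and section 16.1 speaks of up to 120. With another denominator neither 49 nor 51 applies and the interval rule must be recomputed. This is correct, but it makes the stated level more important, because only the interval rule carries over to another denominator.
- **This is a pilot.** Section 16.2 defines no futility stopping rule, the focus is descriptive, and feasibility is also judged qualitatively. All true, yet the section sets these as criteria for the pilot's success and says what fewer than 49 recruits would mean. Such a criterion has to give one answer.
- **Retention need not share the level.** Nothing requires it, and there is no evidence that the retention label is wrong. That also stands. The level for retention should be confirmed deliberately, not changed by default.

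**Conclusion.** The concern holds. The interval printed as exact 90% for 49/120 is the exact 95% interval. Under the 90% criterion as stated, 49 and 50 recruits fail and 51 is the first count to pass, so the printed threshold is two patients too low for its own rule. If 95% was intended, the threshold is right and the label is wrong.

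The discrepancy matters most when the true rate is below the required 50%: at 40%, the choice of threshold changes the chance of passing by 14 percentage points.

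These figures assume exactly 120 patients approached, independent decisions with a common recruitment rate, and the two-sided exact interval that the protocol prints. If the criterion were instead read as a one-sided 90% limit, the threshold would be 53 (52 gives 49.6%, 53 gives 50.4%); the protocol does not say this.

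**What to change.** Choose one level for the recruitment criterion, before the recruitment result is known, and make every figure in section 16.2 agree with it.

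- **Keep 90%.** Require at least 51 of 120, with an exact two-sided 90% interval of 34.9% to 50.4%. State that 50 recruits give an upper limit of 49.6%, and change the failure statement to fewer than 51. The edit is short, but it raises a pre-specified bar: the chance of passing at a true rate of 40% falls from 46% to 32%.
- **Keep 49.** Relabel both the recruitment criterion and the worked interval as 95%. The limits, the count and the sentence about 48 then stand unchanged, and the cost is wording only.

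In either case, state the level for retention explicitly. If it moves to 95% to match, acknowledge that the bar becomes slightly easier (42 instead of 43 followed up, if 60 are recruited). Also say that the interval rule governs, and that the count will be recomputed if the number approached is not 120.

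### The recruitment verdict in 16.2 is a bare count of 49; it can contradict the plan's own interval criterion when fewer than 120 are approached, and 49 is not the 90% cut-off even at 120.

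*Protocol*

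**What the plan says.** Protocol section 16.2 lists two criteria for judging the pilot a success, one on recruitment and one on retention. The recruitment criterion begins as a statement about a proportion: "The upper 90% confidence interval for the proportion of patients recruited should exceed 50" per cent. It is then put as a count with a denominator, "We should recruit at least 49 patients from 120 approached", and justified: "This is based on a requirement that the underlying recruitment rate should be at least 50" per cent. The supporting figures are "The exact 90% confidence interval corresponding to 49 successes from 120 Bernoulli trials is from 32.0% to 50.2" per cent, and "With 48 successes from 120 trials the upper interval drops to below 50" per cent.

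The sentence that gives the verdict has no denominator: "Should we recruit less than 49 patients we would regard this as evidence that the recruitment rate was too low". The section adds that the external validity of a randomised trial would then be in doubt.

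On the denominator, section 16.1 says only that "we believe that is feasible to approach up to 120 patients". No rule is given for a different number approached.

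**The concern.** A count of recruits says nothing about a recruitment rate until it is divided by the number approached. That number is not fixed by design: it is a belief about what is feasible, stated as a maximum. The opening of section 16 lists patient availability and willingness to be randomised as separate things to estimate. A verdict based on 49 recruits alone merges them, so a pilot that found too few patients, most of whom agreed, would be reported as one in which patients would not agree.

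Section 16.2 calls willingness to be randomised the primary purpose of the study, and this is one of only two success criteria. A wrong verdict here bears directly on whether a definitive trial is pursued. The cut-off of 49 also has to be checked against the 90% level that it is said to come from.

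**Working it through.** **Inputs (Protocol 16.1 and 16.2).** Criterion: upper limit of the exact 90% interval above 50%. Count cut-off: 49. Stated limits for 49 of 120: 32.0% to 50.2%. Number approached: up to 120. The numbers approached below 120 used here are assumptions chosen to show a range; the protocol gives no forecast.

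**Formula.** Exact (Clopper-Pearson) interval for x recruited of n approached at confidence 1 − a: lower limit = a/2 quantile of Beta(x, n − x + 1); upper limit = 1 − a/2 quantile of Beta(x + 1, n − x).

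**Step 1: reproduce the plan's figure at n = 120.**

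| Recruited | Exact 90% interval | Exact 95% interval |
|---|---|---|
| 48 | 32.5% to 47.9% | 31.2% to 49.3% |
| 49 | 33.3% to 48.7% | 31.95% to 50.18% |
| 50 | 34.1% to 49.6% | 32.7% to 51.0% |
| 51 | 34.9% to 50.4% | 33.5% to 51.9% |

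The printed 32.0% to 50.2% is the 95% interval for 49 of 120, and the change of verdict between 48 and 49 also occurs at 95%. No 90% version tried reproduces it: the one-sided exact 90% upper limit is 47.1%, the Wald 90% interval is 33.5% to 48.2%, and the Wilson 90% interval is 33.7% to 48.3%. At the stated 90% level, 49 and 50 of 120 pass the count but fail the criterion; 51 is the smallest number that passes.

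**Step 2: the smallest count whose upper limit exceeds 50%, by number approached.**

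| Approached | 90% level | 95% level |
|---|---|---|
| 70 | 28 | 27 |
| 80 | 33 | 31 |
| 90 | 37 | 36 |
| 100 | 42 | 40 |
| 110 | 46 | 45 |
| 120 | 51 | 49 |

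A cut-off of exactly 49 belongs to n = 115 or 116 at 90%, and to n = 119 or 120 at 95%.

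**Step 3: cases where the two rules disagree.**

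- 40/70 = 57.1%, exact 90% interval 46.6% to 67.2%: meets the interval criterion, fails the count.
- 45/80 = 56.2%, 46.4% to 65.7%: the same conflict.
- 48/90 = 53.3%, 44.1% to 62.4%: the same conflict.

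All three observed rates lie above the required 50%, and all three also pass at the 95% level.

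The rules do not disagree everywhere. At n = 100, 30 recruits fail both and 55 pass both; the conflict is confined to counts from 42 to 48 at the 90% level (40 to 48 at 95%).

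**Step 4: chance of the verdict that the rate is too low when the true rate is exactly 50%.** P(X ≤ 48) for X ~ Binomial(n, 0.5):

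| Approached | P(fewer than 49) |
|---|---|
| 120 | 1.8% |
| 110 | 10.7% |
| 100 | 38.2% |
| 90 | 77.0% |
| 80 | 97.2% |

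If the interval is applied to the actual n, this probability cannot exceed 5% at the 90% level or 2.5% at the 95% level, whatever n is, because each tail of an exact interval is bounded by a/2.

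**The case against.** The strongest reply is one of context. The same bullet opens with a criterion on a proportion and attaches 120 to the count three times before the verdict sentence, which itself concludes about a rate. A sympathetic reader would take 49 as the worked case for 120. That reading is available, but the verdict sentence does not state it, the denominator is uncertain, and nothing tells the analyst what to do at another n. A prespecified success criterion should not depend on a generous reading.

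It is also true that the study is descriptive, has no futility stopping rule, and will report a 95% interval for the proportion agreeing to be randomised. Screening logs cover all patients considered. A shortfall in patients approached would therefore be visible. This limits the damage and counts against a high severity, but it does not repair the stated verdict.

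Three stronger readings are tempting and are not supported:

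- A reader might infer that the count gives the wrong answer whenever the number approached is not 120. It does so only for counts between 49 and the cut-off for the actual n. At the 95% level the cut-off is also 49 at n = 119.
- A reader might stress the opposite error, in which more than 120 are approached and 49 passes at a low rate. For example, 49/140 = 35.0% (exact 90% interval 28.3% to 42.2%) would pass the count. The arithmetic is right, but section 16.1 presents 120 as a maximum, so the plan does not foresee this case and the point should not rest on it.
- A reader might infer that 49 is at least correct at n = 120. At the stated 90% level it is not.

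**Conclusion.** The rule is wrong as written, in two linked ways. First, the verdict rests on a count without its denominator, so with fewer than 120 approached it can contradict the interval criterion it is meant to express and report low availability as low willingness. The effect is modest for a small shortfall and decisive for a larger one, as step 4 shows. Second, the cut-off and its printed limits belong to a 95% interval although the text says 90%, so 49 and 50 of 120 pass the count but fail the stated criterion.

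Severity is moderate: this is an end-of-pilot feasibility criterion, read alongside other results, and no treatment decision depends on it. The conclusion assumes that the verdict sentence is applied literally, that the interval is the exact binomial one the plan names, and that fewer than 120 might be approached, which section 16.1 leaves open. The second defect does not depend on how many are approached.

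**What to change.** In section 16.2:

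1. Make the exact interval on the actual numbers recruited and approached the only decision rule, and remove the free-standing verdict on fewer than 49.
2. State one confidence level and correct the printed figures to match it. At 90% the illustration becomes 51 of 120 (34.9% to 50.4%), with 50 of 120 falling short (upper limit 49.6%). At 95% the printed 49 of 120 and its limits stand, and the stated level changes. The choice should be made before the recruitment results are reviewed.
3. Keep the count only as the illustration for 120 approached.
4. Report the number approached against 120 as a separate result on availability.

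Doing item 3 without item 2 would leave 49 of 120 beside a 90% criterion that it does not meet. The cost is a few sentences and no new data, since the screening logs in sections 11.2 and 11.3 already record the patients considered and those who decline.

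### Section 16.2 calls the pilot a success when the target is merely not excluded, so 43/60 (71.7%) retention meets an 80% criterion; the recruitment count of 49 also conflicts with its own interval rule.

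*Protocol*

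**What the plan says.** Section 16.2 introduces two rules with "In addition we will assess whether the following criteria for evaluating the success of the pilot have been met".

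- **Recruitment:** "The upper 90% confidence interval for the proportion of patients recruited should exceed 50" per cent. The protocol adds "We should recruit at least 49 patients from 120 approached", and explains: "This is based on a requirement that the underlying recruitment rate should be at least 50" per cent. It prints an exact 90% interval of 32.0% to 50.2% for 49/120, notes that 48/120 falls short, and says that fewer than 49 recruits would be taken as evidence that the rate is too low.
- **Retention:** "The upper 90% confidence interval for the retention rate", defined as those followed up out of those recruited, has to reach 80% or more. There is no minimum count, no minimum observed rate and no statement of what failure would mean.

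On size, section 16.1 says "We aim to recruit a total of 60 patients (30 to the surveillance arm; 30 to the ablation arm") and that it is "feasible to approach up to 120 patients". Section 9.1 makes recruitment and retention rates the quantitative part of the primary outcome.

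**The concern.** Reaching a target with the upper confidence limit is weak evidence. It says that the data have not ruled the target out, not that the target has been met. Section 16.2 nevertheless calls this success and links the recruitment version to a requirement on the underlying rate. These criteria are the only quantitative decision rule for the primary outcome, so a pilot clearly short of its retention target could be reported as having met it.

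The recruitment bullet has a further problem. It states one rule twice, as an interval and as a count, and the two can give opposite verdicts on the same data.

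**Working it through.** **Inputs (sections 16.1 and 16.2).** Targets 50% and 80%; exact interval labelled 90%; 120 approached; 60 planned recruits; 49 minimum recruits.

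**Formulas.** Exact (Clopper-Pearson) limits for x out of n, with a = 0.10 for a 90% interval or 0.05 for 95%:
- lower = a/2 quantile of Beta(x, n − x + 1)
- upper = 1 − a/2 quantile of Beta(x + 1, n − x)

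The probability of passing is the binomial tail P(X ≥ c), where c is the smallest passing count.

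**1. The plan's own figure.**

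| x/120 | exact 90% | exact 95% |
|---|---|---|
| 48 | 32.5% to 47.9% | 31.2% to 49.3% |
| 49 | 33.3% to 48.7% | 32.0% to 50.2% |
| 50 | 34.1% to 49.6% | 32.7% to 51.0% |
| 51 | 34.9% to 50.4% | 33.5% to 51.9% |

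The printed 32.0% to 50.2% is the 95% interval, and the remark about 48 is also true at 95%. At the stated 90% level 49 fails and the smallest passing count is 51.

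**2. Retention, upper exact 90% limit at least 80%.**

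- n = 60: 42 gives an upper limit of 79.6% (fails); 43 (71.7%) gives 60.6% to 81.1% (passes).
- n = 49: 33 gives 78.3% (fails); 34 (69.4%) gives 56.8% to 80.1% (passes).

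| True retention | P(pass), n=60, c=43 | P(pass), n=49, c=34 |
|---|---|---|
| 65% | 0.17 | 0.31 |
| 70% | 0.45 | 0.61 |
| 75% | 0.78 | 0.86 |
| 80% | 0.96 | 0.97 |

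If 95% was the level intended throughout, the passing counts fall to 42/60 (70.0%) and 33/49 (67.3%).

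**3. Recruitment with fewer than 120 approached (80 as an illustration).**

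- 33/80 = 41.3%, exact 90% interval 31.9% to 51.1%: meets the interval rule, fails the count.
- 48/80 = 60.0%, interval 50.2% to 69.2%: the whole interval lies above 50%, yet 48 is below 49.

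**4. Operating characteristics of a go rule on observed rates.**

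- Recruitment, at least 60/120: P(go) = 0.54 at a true 50%.
- Retention, at least 48/60: P(go) = 0.06 at a true 70%, 0.23 at 75%, 0.58 at 80%, 0.89 at 85%.
- Both, if independent and exactly on target: 0.536 × 0.576 = 0.31.
- Amend zone when on target, with 90% stop boundaries (51/120 and 43/60): 0.959 − 0.536 = 0.42 for recruitment; 0.957 − 0.576 = 0.38 for retention. Stop is about 0.04 for each.

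**The case against.** The best defence is that these are screens. Section 16.2 presents the recruitment rule as a check for evidence that the rate is too low, and expects the qualitative work to improve disappointing rates. Failing a small pilot only when the target is excluded is coherent, and it passes a true 80% retention 96% of the time at n = 60. That stands as a defence of the rule as a stop boundary. It does not justify calling the result success when no separate standard for going ahead is given.

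It may also be said that the count of 49 is conditional on 120 approached. The sentence naming it is, but the following statement about recruiting fewer than 49 carries no such condition, and section 16.1 gives 120 as a maximum.

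Three stronger readings are tempting and are not supported:

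- **That the retention bar keeps falling as recruitment falls.** Taken alone, the rule would pass 20/30 (66.7%). But the two criteria are listed together. If both must hold, with 120 approached, the protocol's own count keeps n at 49 or more, so the bar moves only from 71.7% to 69.4%. Nor is the fall strictly monotone: n = 40 needs 28 (70.0%).
- **That poor retention generally has an even chance of passing.** That describes a true 70% at n = 60; at 65% the chance is 0.17.
- **That the definitive trial would then be planned on 80%.** Section 16.2 reports observed proportions with 95% intervals, and section 16 says that the estimates inform the later trial. Nothing carries 80% forward.

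**Conclusion.** The point holds in three limited parts.

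1. Success is the wrong label for a target that is merely not excluded. At the planned 60 recruits, retention can be 8.3 percentage points below target (80 − 71.7) and still pass.
2. The fixed count and the interval rule for recruitment conflict whenever appreciably fewer than 120 are approached.
3. They conflict at 120 as well, because a 95% interval is labelled 90%.

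The figures assume exact two-sided limits, as in the protocol's worked example. On a one-sided 90% reading the n = 60 pass mark would be 44 (73.3%), which leaves the conclusion unchanged. The pass probabilities assume independent patients with a common retention rate. The issue affects how feasibility is declared, not any treatment estimate, so it should be corrected but does not undermine the pilot's data.

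**What to change.** Replace the two criteria with three zones:

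- **Stop:** the upper confidence limit is below target, so the target is excluded. This is the present rule under its proper name.
- **Go:** observed recruitment is at least 50% of those approached, and observed 6-month retention is at least 80% of those randomised.
- **Amend:** anything between; proceed only with changes drawn from the qualitative work.

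State recruitment as a rate on the number actually approached, keeping any count only as the worked example for 120. Correct that example by relabelling the interval 95% (count 49) or keeping 90% (count 51). Say whether the same level applies to retention, because the choice moves its stop boundary between 43/60 and 42/60.

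The change takes a few lines and no new data. Its cost should be stated beside it: with true rates exactly on target, go is reached with probability about 0.54 for recruitment (n = 120) and 0.58 for retention (n = 60), about 0.31 for both if independent, and otherwise the result is mostly amend. The stop boundary still depends on sample size, so the numbers approached and randomised should be reported with the decision.
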